#### **Dental Tobacco Control.net (DTC.Net): Improving Practice ([name], PI)**

This NIDA-funded randomized trial (R01-DA-017971) is in its fourth year. We have developed an interactive Internet-delivered intervention designed to encourage dental providers to increase tobacco control activities in their practices. This study is directly relevant to the current proposal in that 1) we have developed a series of interactive provider education modules and a toolbox of useful materials that can be easily adapted as supplementary provider education for our proposed intervention (see Appendix A for screenshots), 2) we have demonstrated success in recruiting 190 practices to participate in the project, 3) we have demonstrated the ability to recruit patients at the time of their office visit in these practices, and 4) in preliminary analysis, we have demonstrated that the providers in the provider intervention have increased quit smoking advice rates.

Three hundred practices across four southern states, North Carolina, Georgia, Alabama and Florida, completed an initial interest survey. To blind participants to the specific tobacco control target, the intervention was described as an "Online Study Club for Oral Cancer Prevention." Interested practices were asked to complete a run-in phase where patient & practice data were collected and returned.

[figure not shown]
Success in recruiting practices - Of the 300 initial practices, 208 (69%) returned baseline data, and 95 intervention, 95 control were finally randomized. In DTC.Net, the 95 intervention practices were encouraged to logon and participate in the intervention. To date, 128 dentists and hygienists have logged onto the website. The total number of visits to the website since it was launched in June 2005 is 398 (28 visits per month).

Figure 2 displays the number of visits over time, with spikes that coincide with email marketing of new website content. This demonstrates our success in developing website “stickiness” or retention (See Appendix B).

Recruiting patients to assess providers

We developed “patient exit cards” – brief surveys completed by patients at the end of their appointment – using principles of ecological momentary assessment. The exit cards were designed to be completed in one to two minutes. The patient exit cards serve as our main outcome: a patient-reported performance measure of the provider’s delivery of tobacco cessation advice.

Of the 19,000 exit cards distributed by our 190 practices, 15,575 (82%) were returned with usable data at baseline. From these data, patients agreeing to a follow-up were part of a brief validity assessment at six of the practices. We contacted 161 patients by phone (1% sample) and found that patient’s age, gender, and smoking status agreed in 98%.

Preliminary Analysis of Outcomes - To date we have entered follow-up data on 143 practices (76%), with a patient response rate similar to that at baseline (82% (9,498/11,600)).

The intervention has been successful at increasing advice (Table 4). At eight-months of follow-up, intervention practices increased cessation advice by 11%. When adjusting for patient age, gender, frequency of smoking, and clustering of patients within practices using generalized estimating equations, intervention patients were again more likely to receive quit tobacco advice (Adjusted Odds Ratio 1.6 (95% CI 1.3-1.9)).

Using a group by time interaction term, we found that intervention practices significantly improved compared with control practices for ADVISE (p = 0.042).

The practice-level intraclass correlation coefficient for ADVISE was 0.15, estimated using one-way ANOVA.

This was very similar to an ICC reported for tobacco use screening by Eccles. In DTC.Net, we have also estimated six-month patient tobacco-cessation rates using a telephone-based follow-up survey that can be used to estimate the intra-class correlation coefficient for tobacco-cessation rates within dental practices. One-way ANOVA analysis of this survey data estimated an ICC of 0.017 (95% CI 0.00-0.10) indicating that only 1.7% of the variance in cessation was accounted for by the dental practices.

	Pre-Intervention	Post-Intervention
Intervention	44% (710/1,611)	55% (748/1,361)
Control	42% (488/1,169)	45% (545/1,210)

**Smoking Coach: An Internet-tailored Intervention** ([name], PI; [name], co-PI)

In this NCI-funded R21 proposal, we designed and evaluated the “Smoking Coach” - an Internet-delivered, tailored, public health intervention for smoking cessation that not only included self-help strategies, but also encouraged seeking social support (Family Info) and help from health care providers (Doctor Info) (See Appendix C for screenshots). In this project, we began with a formative evaluation. Critical themes from focus groups included: make funding transparent (not affiliated with tobacco companies), provide at no cost to users, and improve the site name. The participants unanimously did not like the name “Smoking Coach” (too over-bearing). We then developed the site based on this formative research and using constructs from multiple behavioral theories including health belief model (HBM), social cognitive theory (SCT), and the transtheoretical model (TM). Reviewers can access the website at [www.free2quit.cme.uab.edu](http://www.free2quit.cme.uab.edu) and login using the name: “reviewer.” Although we cannot duplicate all the website content within the text of this

Principal Investigator/Program Director (Last, First, Middle): DPBRN c/o [name]

proposal, specific examples of how we used behavioral theory include: 1) using a personal story of a smoker for vicarious learning (SCT); 2) providing “How close am I to Quitting?” (Decisional Balance –TM) and “What do I need to overcome?” (Temptations – TM) calculators – interactive assessments with tailored feedback; 3) Risks to My Body (Perceived Susceptibility – HBM); and 4) supporting a smoke-free home around the time of quitting (Environment/Reciprocal Determinism – SCT). The components of the website work together to motivate those not quite ready to quit and to provide targeted strategies for those preparing to quit.”

After initial development, two groups of current smokers were recruited using targeted advertisements on Google (May 2004 and February 2005). Smokers logged onto the website, consented to participate, and completed an introductory questionnaire that resulted in dynamic tailoring of the website. In Phase 1, we assessed usage patterns of 126 smokers. We noted that few participants used the family and doctor info (Table 5). After reviewing these statistics, we added an introductory page to the website with additional content encouraging use of all components. The introductory paragraph included actual data from previous users, encouraged users to use all components of the website, and was signed by the two physicians associated with the study.

Outcomes Assessment - In Phase 2, 212 smokers were randomized to a control website that was linked to other smoking information online (www.smokefree.gov) or to the intervention. Phase 2 trial participants (N = 212) were mostly female (68%), white (80%), and relatively young (63% less than 45). Time spent on the website and use of the family and doctor modules increased, compared with Phase 1 (Table 5).

Phase 2 smokers were then re-contacted by telephone in one month to assess smoking status. Sixty-four participants completed the one month follow-up assessment, and we found no

differences in age, gender, education, or previous quit attempts among those with follow-up and those lost. In intent-to-treat analysis, 9% (9/105) of intervention participants quit smoking compared with 3% (3/107) of the control group (p = 0.069). In an analysis based only on those who completed the follow-up assessment (n=64), a higher percentage of the intervention group reporting quitting (9/31=29%) compared to the control group (3/33=9%, Fisher’s Exact p = 0.055). After adjustment for age, gender, and income, intervention users were still more likely to quit (Odds Ratio = 4.3 (95% CI 1.0 – 20.5)) compared with control. Because users varied in their intensity of using the website, we also looked for a *dose-response* effect. Compared with the control, low-level users (lowest quartile of use) had a small benefit (OR 2.5 (95% CI 0.2-30)), and higher level users were higher (4.44 (CI 1.04-18), p for trend = 0.04).

Among those who completed follow-up, 100% of the intervention group spoke with their family about quitting compared to 87% of the control group (p = 0.045), but no significant difference was seen in talking to a doctor (38% intervention versus 42% control, p = 0.7). Overall, 36% of the 64 users who participated in follow-up used nicotine replacement and 10% used bupropion, with no differences by experimental group (intervention versus control p > 0.5 for both). Thus, although we demonstrated some modest success, the website was limited in that we were not successful in increasing treatment seeking among these patients. The manuscript for this study is currently under review.

These **two studies** highlight our expertise and prior success in demonstrating acceptability and feasibility of Internet-delivered smoking cessation interventions. They also identify the real boundaries to these prior experiments. **The current proposal does not represent a marginal improvement of this prior work, but a paradigm shift focusing on the clinical microsystem and using the automation and full integrative power of the Internet.** Our intervention can be defined as a complex intervention to improve health. Following the framework for evaluation of complex interventions, this study is built on the previous exploratory trials, and designed as a definitive randomized trial in the real-world of clinical microsystems.

	Phase 1 (n = 126)	Phase 2 (n = 105)
	%	%
Used Specific Module		
Used Self-Help Strategies	58	69
Used Family Info Module*	29	50
Used Talking to your Doctor Module*	33	56
Time Spent on Website (Minutes) *		
Less than Three Minutes	31	24
Three to Ten Minutes	30	13
Over Ten to Twenty-five Minutes	15	31
Over Twenty-five Minutes	23	32

\* p < 0.001 (comparing Phase 1 and Phase 2)

**D. RESEARCH METHODS****D1. Overview, Task List, and Timeline**

Our task list (Table 6) is organized into 6 categories: 1) intervention refinement and programming; 2) usability testing; 3) recruitment and retention of dental practices; 4) intervention maintenance; 5) data collection; and 6) analyses. As discussed in Section A, we evaluate the process of care.

The combination of the patient and hygienist internet interventions is entitled HI-QUIT (hygienists' internet quality improvement in tobacco cessation). HI-QUIT is conceptualized in two components: Refer2Quit and Decide2Quit (See Figures 4 and 5). Major innovations are the microsystem integration of the patient referral portal (Refer2Quit) and the hygienist education system. We will conduct a randomized controlled trial (RCT) to ascertain the efficacy of this multi-modal intervention in improving smoking cessation processes of care and patient outcomes. In relation to the smoking cessation impact of HI-QUIT, this trial is defined as a cessation-induction study – a test of treatment to prompt cessation among all smokers, including those who are not currently trying to quit.

Studies of complex microsystem interventions are inherently complex and require detailed evaluations. In addition to our quantitative hypothesis-driven analysis, we will also conduct a secondary process analysis case-comparison of intervention practices with varying rates of adoption of HI-QUIT. The proposed intervention is designed to have a layered effect – changing hygienist performance (including advising smokers to quit and referring them to a self-management website) and also patient behavior (including going to use the website and ultimately quitting smoking). Thus, our analyses are designed to understand the intervention from each of these “layers” – from the patient and hygienist perspective.

Table 6: Task List		Study Months	1.Intervention Refinement	2.Usability Testing	3.Recruitment - Retention	4.Intervention Maintenance	5.Data Collection	6.Analyses
1	Finalize recruitment plan and website plan	1-3	X	X				
2	Program Refer2Quit hygienist website	2-7	X					
3	Program Decide2Quit intervention patient website	2-7	X					
4	Conduct final usability testing by patients and hygienists	6-7		X				
5	Finalize website based on usability tests	7	X					
6	Develop and finalize investigators web “admin” portal	7	X	X	X			
7	Activate HI-QUIT	7				X		
8	Send mass mailing to identify interested providers	6-10			X			
9	Enroll/randomize providers (Intervention Time 0 (I0))	6-10			X	X		
10	Collect baseline practice data online	7-23					X	
11	Complete practice run-in phase data (exit cards)	7-23					X	
12	Send repeated emails to dentist/hygienist for retention	7-23			X		X	X
13	Collect usage data from websites	7-23	X		X		X	X
14	Have practice enroll patients through Refer2Quit	7-23			X	X		
15	Send provider reports of patient enrollment	7-23				X	X	
16	Measure Referral Rates at baseline, 6 and 12 months after practice enrollment using patient exit card surveys (first cards collected in run-in phase)	7-12					X	H1
17	Measure number of referrals using Refer2Quit and Information prescriptions	7-23						H1
18	Measure rates of patients who GO to Decide2Quit	7-23					X	H2
19	Measure patient QUIT rates, quit attempts, and readiness to quit at 6 months (telephone follow-up)	10-30						H3
20	Validate 6-month quit with Cotinine*	10-30					X	H3
21	Test Hypotheses, prepare manuscripts	10-36						X

\*Mailed salivary cotinine (Salimetrics); H1 = Hypothesis1; H2 = Hypothesis 2; H3 = Hypothesis 3 (See D5 for details of Measures)

To further clarify the flow of the development, intervention, and evaluation, Figure 3 below summarizes the planned timeline for accomplishing key tasks.

[figure not shown]

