**D8. Main Evaluation Measures**

As depicted in Figure 4, HI-QUIT is designed to have a sequence of effects on the process of care within each clinical microsystem. Thus, we have designed our main evaluation to assess several key areas of influence that we have abbreviated as **Refer -> GO -> QUIT**. For our hypotheses, we have three primary dependent variables. Each of the outcomes is collected at the patient level and is used to create a proportion. The first link in the chain of evaluation is of course to assess the performance of the provider. We will use the exit cards to assess the proportion of smokers who are referred. This is assessed at discrete time points (Patients recruited in 3 cohorts at intervention Time 0 (I0) (pre-intervention), I0 + 6 months, I0 + 12 months,).

This analysis is solely to assess provider performance and data are collected from patients anonymously. The proportion of smokers who are referred who GO to the website (H2), and the subsequent

Table 10: Dependent (outcome) variables (Refer -> GO -> QUIT)					
Label	Question	Source	Collected	Numerator	Denominator
Refer (H1)	During your provider’s visit TODAY did anyone: Refer you to Decide2Quit* - a website with information about tobacco?	Patient Exit Card	Discrete Intervals (baseline, 6 and 12 Months)	Number Referred	Number of Smokers
GO (H2)	Proportion of patients from the practice who log onto website	Website tracking and information prescriptions	Continuous	Number who GO	Number Referred ‡
QUIT (H3)	Do you currently smoke cigarettes (smoked even 1 puff in the last 7 days)?	6 month survey†	Continuous	Number who QUIT	Number Referred ‡
* control website for Controls; † validated using mailed cotinine saliva kit. ‡ Assessed by web tracking in intervention, in control by leave-behind receipts from information prescriptions					

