Cotinine biochemical verification: In 2002, the SRNT Subcommittee on Biochemical Verification published recommendations and evidence to aid the decision-making in choosing biochemical verification. This article divided studies into clinic-based trials (usually with less than 500 participants) where misclassification is higher and the need for biochemical verification is high and participation in biochemical verification is also high, versus population-based studies where misclassification is low and biochemical verification is less needed, and is in fact less feasible (with non-response rates up to 70%). In planning the study, we feel that HI-QUIT is closer to a clinic-based trial. The connection to the clinical microsystem makes this study more intense than public health interventions and may change the demand characteristics. To increase participation rates for the mailed salivary cotinine, we will provide an additional incentive of \$50 for completing this sample. However, we acknowledge that not all patients may complete cotinine validation by mail. For patients who self-report quitting at six months, but fail to return their cotinine saliva sample, we will use their self-report data, acknowledging that those who do not return their cotinine sample will be more likely to mis-report cessation. We will carefully assess for differential misclassification comparing intervention and control. First, we will compare participation rates for returning the cotinine sample by intervention and control. Next, we will assess self reported cessation among those that do and do not return the cotinine sample (comparing intervention and control). Finally, we will compare the misclassification rates among those that did return the sample (again intervention vs. control). If differences are detected, this would represent a case of non-ignorable missing data. Using these rates, we will conduct sensitivity analyses to assess the impact of differences in participation and misclassification on our main outcome and use pattern mixture approaches to assess how much our main analysis might change.

**D9. Analysis Plan:** For each practice, HI-QUIT is available for 20 months (see Figure 3, section D1). We plan to assess the impact of the intervention throughout this interval.

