For patients referred by hygienists using refer to quit, patient consent is layered and matched to the risk and burden to the patient. Patient consent is not obtained at chairside after they agree to be enrolled. At this level of participation, only patient email is collected. Intervention patients will receive emails after being referred to the intervention website by providers. To minimize risk, the emails will only contain a reminder to go to the website, but will not identify the purpose of the website. No personal health information will be in the emails. Because risk is low and it is not feasible to obtain informed consent without changing the processes of care themselves, we will not obtain informed consent at this level (similar to prior Fax-to-Quit studies).

If patients choose to log onto the web-based system, they will be asked to complete an online consent process where they agree to specific line items (agree to allow us to track their use of the site, agree to follow-up) by online check boxes verified with a username and password they create. If they agree, they will provide telephone numbers for follow-up. If they do not wish to participate in follow-up, they can use the online system without providing additional identifying information. Because participation is again optional, and because requiring written consent would likely greatly decrease use of the online system, we will not obtain written informed consent at this phase. Once the patient is called for follow-up, we will complete a verbal consent procedure for participating in the interview. If the patient reports smoking cessation, we will obtain written informed consent when the specimen is collected. Thus, signature documentation is only obtained for the subset of patients for whom biologic specimens are obtained. This layered procedure has been used in prior studies including DTC.Net and the NCI-funded Smoking Coach study referenced in the application.

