#### For Phone Interviews (Follow-up assessment of website participants to assess smoking cessation (H3):

Research assistants will obtain verbal consent to participate in the brief telephone survey. For quality assurance of data collection, a ten percent sample of telephone surveys will be audiotaped. The selected patients will also be asked if they are willing to be audiotaped. If the patient declines to be taped, they will be allowed to participate in the interview without the audiotape.

Patients who have quit at six months will be asked if they agree for us to mail them a saliva test kit for a salivary cotinine sample. If they consent, a collection tube from Salimetrics and instructions for use will be sent. The patient will mail the collection tube directly to the lab in a postage-paid envelope.

Risks to patients also include the burden of completing the exit interviews and follow-up surveys. We will provide a small compensation to offset the effort of participating in the follow-up telephone interviews and cotinine validation. Patients may certainly benefit from the training their providers have received in the form of more appropriate counseling.

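### The cotinine sample is collected at an unrecorded time after the six-month call, so the planned misclassification rate mixes later relapse with misreporting

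*Protocol*

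**What the plan says.** The task. Table 6 in D1 lists, as task 20, "Validate 6-month quit with Cotinine".

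The outcome. Table 10 in D8 bases QUIT on the question "Do you currently smoke cigarettes (smoked even 1 puff in the last 7 days", asked in the six-month survey. D9, Hypothesis 3, repeats it. QUIT therefore describes the week before the call.

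The sample. Section E, under Phone Interviews, puts the kit after the report: "Patients who have quit at six months will be asked if they agree for us to mail them a saliva test kit". Then: "If they consent, a collection tube from Salimetrics and instructions for use will be sent", and "The patient will mail the collection tube directly to the lab in a postage-paid envelope". The only patient record described at collection is a consent: "If the patient reports smoking cessation, we will obtain written informed consent when the specimen is collected". No maximum interval, collection date or repeat smoking question is described.

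The use made of it. The D8 text on cotinine verification first compares kit return by arm, then self-reported cessation in returners and non-returners. The third step is: "Finally, we will compare the misclassification rates among those that did return the sample". If arms differ, D8 treats the data as non-ignorably missing and uses the rates in sensitivity and pattern-mixture analyses of the main outcome. Where no sample comes back, the self-report is kept.

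The H3 count. In both the primary and the secondary analysis, D9 takes as numerator the patients who report cessation at the six-month calls.

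**The concern.** Cotinine reflects recent nicotine exposure, so the result speaks to the days before collection, a later window than the one QUIT describes. D8 has one reading for a disagreement: the patient misreported. It has no category for someone who answered truthfully at the call and smoked again before the tube was filled.

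Kits go only to people who reported quitting, so this error runs one way: it can only raise apparent misreporting. The $50 incentive in D8 is for completing the sample, so relapse does not remove the reason to return one.

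What is at stake is the D8 safeguard. Its rates are meant to show how far the H3 result could depend on false reports, and whether that differs by arm. If they also contain post-call relapse, they answer a different question. Without date and status recorded at collection, no later analysis can separate the two.

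**Working it through.** **1. Sequence and windows, from the protocol**

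- Call at six months: the patient reports on the previous 7 days (D8 Table 10; D9).
- After a reported quit: kit offered, agreed to, mailed, used, and posted to the laboratory (Section E). The interval is positive and of unstated length.
- Result: nicotine exposure shortly before collection.
- Reading: a mismatch is misclassification (D8).

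**2. Effect on the misclassification rate**

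Among returners, let m be the fraction who misreported at the call and r the fraction of truthful reporters who resumed before collection and test positive. Then

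apparent rate = m + (1 − m) × r.

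The inflation is (1 − m) × r, which is close to r when m is small. The documents give neither m nor r.

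**3. Illustrative range for r (assumptions, not protocol figures)**

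With weekly resumption w and delay t weeks, r = 1 − (1 − w)^t.

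- w = 2%, t = 1: r = 1 − 0.98 = 2.0%.
- w = 5%, t = 4: r = 1 − 0.95^4 = 1 − 0.8145 = 18.5%.

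If nobody misreported (m = 0), D8 would still show 2 to 18.5% misclassification. On the Table 11 counts, with every kit returned:

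- intervention: 120 × 0.02 = 2.4 to 120 × 0.185 = 22 patients;
- control: 20 × 0.02 = 0.4 to 20 × 0.185 = 3.7 patients.

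**4. Effect on H3**

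The planned figures reproduce: 120/1,920 = 6.25% and 20/960 = 2.08%, shown as 6% and 2% in Table 11. The difference is 4.17 points and the ratio 3.0.

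*D9 as written.* The numerator is the report at the call. A later relapse changes no count: 6.25% v 2.08% stands.

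*A sensitivity analysis that removes quits at the apparent rate.* D8 does not give the form of this analysis. Assume the rate is applied to all reported quits, with m = 0 and r equal in both arms, so each proportion is multiplied by (1 − r):

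| r | Intervention | Control | Difference |
|---|---|---|---|
| 2% | 6.13% | 2.04% | 4.08 points |
| 18.5% | 5.09% | 1.70% | 3.39 points |

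The ratio stays 3.0. The same figures result if every kit is returned and positive samples recode patients as smokers. With r = 20% and full return, power at 30 practices per arm (ICC 0.017; 48 and 24 referrals per practice) is still about 91%.

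*Unequal kit return, again only if positives are recoded.* With r = 10% and assumed return of 70% v 40%: 120 × (1 − 0.10 × 0.7)/1,920 = 5.81% and 20 × (1 − 0.10 × 0.4)/960 = 2.00%. The misclassification rate among returners would be 10% in both arms.

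**The case against.** **Does it affect H3?** A reader might infer that patients who resume after the call are removed from the quitters, so that an arm difference in kit return becomes an arm difference in QUIT. The documents do not support that. D9 fixes the numerator as reports at the calls, and nothing says a positive sample turns a quitter into a smoker. There are hints: D7 says cessation will be validated by cotinine, Table 10 labels the outcome validated, and D8 keeps the self-report specifically when no sample returns. These make the rule unclear; they do not establish recoding. D8 also already compares kit return by arm.

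**Is there really no question at collection?** A reader might take the protocol to exclude one. It does not. The kit instructions and consent form are not shown, so one can say only that none is described. But this item cannot be left to a later analysis plan, because it must be collected with the sample.

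**Would it mislead the arm comparison?** D8's further step is triggered by a difference between arms, and equal relapse raises both rates alike. That stands. Intervention patients receive email reminders that control patients do not (D3), so equal relapse is not assured, but the protocol supports no particular difference. Over-correction of H3 is possible, not shown.

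**Is the lag inherent in mailed verification?** Yes. That argues for recording it.

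**Would repeating the question alone be enough?** No. In the Smoking Coach data (Section C), 36% of the 64 followed-up users used nicotine replacement. An honest non-smoker on such a product can test positive, so the misreport definition must allow for that.

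**Conclusion.** The point holds for the misclassification rates in D8 and the analyses built on them. The sample follows the window it is meant to validate by an unlimited and unrecorded interval, and a mismatch has only one reading. The apparent misreport rate is raised by roughly the fraction of truthful quitters who resume before collection. The documents do not give its size; 2 to 18.5% rests wholly on the assumed delay and weekly resumption.

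The H3 counts as D9 defines them do not move. They would move only if positive samples recode quitters. Even then, with equal relapse and full return, the difference would fall from 4.2 to between 4.1 and 3.4 points under these assumptions. Severity is minor: a sensitivity check is weakened and the primary count, read literally, is not. What D7, D8 and D9 intend a positive sample to do should be settled in the text.

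**What to change.** On the form enclosed with the kit, record the collection date, repeat the 7-day smoking question, and ask about current use of nicotine products.

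In D8:

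- count as a misreport only a positive sample from a patient who claims abstinence and reports no nicotine-product use at collection;
- report the call-to-collection interval by arm;
- show the misclassification rates, and the analyses that use them, both with and without patients who report resuming after the call.

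Reconcile D7, Table 10 and the cotinine text in D8 with the numerator in D9, stating whether a positive sample changes QUIT.

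The cost is three items on a form sent with a kit that is already mailed, and a few sentences in D8, with no extra contact. The downside is that some patients may explain a positive sample by claiming a later relapse, which is why both sets of rates are needed.
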